17.3.2. ANALYSIS OF EXPLORATORY EFFICACY VARIABLES

The iRECIST BOR will be presented using contingency tables with absolute and relative frequencies.

Additionally, an alternative spider plot will be produced. This will be the same as described in section 17.2.3.2 except the profile will continue until iRECIST iCPD, death or lost-to-follow up, whichever occurs first. Each patients iRECIST BOR (or CA-125 response if no RECIST evaluation available) will displayed.

All efficacy data recorded in the following eCRFs will be listed: tumour marker, target lesions assessment, non-target lesions assessment, new lesions – RECIST, new lesions – iRECIST, overall response – RECIST and overall response iRECIST.

18. SAFETY OUTCOMES

All outputs for safety outcomes will be based on the SAF analysis set except the DLT summaries and listing which will be on the RP2D analysis set.

Document: T:\sas\Debiopharm\Debio_1143\CZA60507\Biostatistics\Documentation\SAP\SAP Text\V5

Author: XXXXXXXXXX Version Number: 5.0
Version Date: 19APR2022

Template No.: CS_TP_BS016 Revision 5
Effective Date: 01Apr2018

Reference: CS_WI_BS005

Copyright © 2009, 2010, 2012, 2016, 2018 IQVIA. All rights reserved. The contents of this document are confidential and proprietary to IQVIA Holdings Inc. and its subsidiaries. Unauthorized use, disclosure or reproduction is strictly prohibited.

18.1. ADVERSE EVENTS

AEs as recorded in the Adverse Events eCRF will be coded using the most up-to-date version of the MedDRA central coding dictionary at the time of analysis.

TEAEs are defined as AEs that started or worsened in severity on or after the first dose of any study medication and prior to the last date of nivolumab + 5 months or the earliest date of new anticancer therapy – 1 day, whichever occurs first.

See section 8.2.1 for handling of partial dates for AEs. In the case where it is not possible to define an AE as treatment emergent or not, the AE will be classified by the worst case; i.e. treatment emergent.

AEs will be graded according to NCI-CTCAE version 5.0

An overall summary of number of subjects within each of the categories described in the sub-sections below, will be provided as specified in the templates.

Listings will include TEAEs, Non-TEAEs and TEAEs leading to discontinuation of Debio 1143.

18.1.1. ALL TEAEs

TEAEs will be presented by the following:

- System Organ Class/Preferred Term (SOC/PT, by cycle)
- SOC/PT & worst grade (by cycle)
- SOC/PT & worst grade (by cycle for cycle ≥ 2 , updating denominator for each cycle with the number patients receiving at least one dose of nivolumab in that cycle)
- PT & pooled worst grade (pooling grade 1-2 and grade 3-4)

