If a patient does not meet the requirements for treatment continuation on any day other than D1 (D2-10 or D15-24) of any cycle, treatment will be immediately interrupted and the corresponding Debio 1143 dose (and nivolumab if on D15) will be omitted. Patients should be re-assessed, ideally, every 48-72 hours, if clinically indicated, and treatment will only be resumed after all re-treatment criteria are met. On D1, treatment can be delayed more than 3 days if required; in this case, the assessment schedule will shift accordingly, and all assessments planned for D1 will be performed on the day treatment is re-started. However, if treatment is interrupted during any day other than D1 and the re-treatment criteria are not met within 72 hours, treatment will be resumed only on D1 of the next cycle.

A maximum delay of 4 and 8 weeks (+1-week tolerance) for Debio 1143 and nivolumab, respectively, is allowed. After this delay-period, treatment will be withdrawn. Patients withdrawing from treatment for any reason will be followed for safety up to 5 months (±15 days) after the last nivolumab infusion, complete resolution or stabilization of any ongoing toxicity, unless the patient starts a new treatment, end-of-life-care or withdraws consent.

Patients experiencing immune-related AEs, that require withholding nivolumab infusions temporarily until resolution to at least Grade 1, may withhold nivolumab for a maximal period of up to 8 weeks (±1 week

tolerance). During this period, patients may continue to receive Debio 1143 as per protocol, if appropriate. Patients requiring more than 8 weeks ( $\pm 1$  week) of nivolumab interruption and those who permanently discontinue nivolumab for any reason, will discontinue Debio 1143 permanently and will be withdrawn from the study. The nivolumab dose will not be adjusted under any circumstances.

Patients experiencing any treatment-related grade 4 toxicity (clinically or laboratory, excluding grade 4 amylases and/or lipase and/or non-febrile neutropenia) will withdraw from treatment definitively without further reduction (see [section 8.3.2.1](#) for details).

Patients experiencing any other treatment-related toxicity fulfilling applicable DLT criteria (as shown below) at any time during the study must stop treatment and may only resume treatment after adequate recovery to re-treatment criteria.

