### 11.6.4. Final analysis

The final analysis will be performed within one year of the End of the Main study period (which lasts until 18 months after LPI or 60 days after last LPLV, whichever occurs first).

Data collected after the Main study period for patients entering the Extended study period, will be summarized using descriptive statistics and included in an addendum to the Final CSR.

The main study results will be presented separately for both study parts. An exploratory analysis will be conducted by pooling demographics, baseline characteristics and safety, data from both study parts. In addition, if homogeneity tests allow, and any specific cohort population is adequately represented in Part A, efficacy data from both study parts may be pooled exploratory, as appropriate.

In Part B, according to the Bayesian posterior probability used in each non-futile cohort at the final efficacy assessment conducted in the 15 evaluable patients, the first proof of efficacy will be claimed if at least four confirmed responses are reported in these 15 evaluable patients. This efficacy boundary was derived assuming a confirmed ORR of 15% and a probability confidence threshold of efficacy of 80%.

A homogeneity test of the primary endpoint will be conducted in the non-futile cohorts showing a confirmed response rate of at least 15%. In case of homogeneous response rates across the cohorts, efficacy data will be pooled and all the efficacy endpoints will be reported overall and by cohort. Otherwise, the efficacy will

be reported by cohort only. The efficacy of the futile cohorts and of the cohorts with less than 15% response rate will be reported separately.

All other endpoints such as demographics, baseline characteristics, safety, PK, PDy, etc. will be presented overall and for each cohort.

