4.3. CHANGES TO ANALYSIS FROM PROTOCOL

Screened Analysis Set

The protocol does not mention a screened analysis set but it has been included in this SAP for the purposes of subject disposition analyses.

Analysis of primary endpoint (ORR)

The protocol mentions reporting ORR at final analysis in terms of relative and absolute frequencies along with a 95% confidence interval. As this is a Bayesian analysis, we need to provide an estimate of the ORR based on the posterior beta distribution along with a 95% credibility interval. This has been described in section 17.1.3.

Pharmacokinetics

Graphical presentation of concentration-time profiles is simplified to depict geometric mean concentrations \pm geometric standard deviations and individual profiles on log₁₀/linear scales.

For the non-compartmental PK analysis, in addition to the analysis for plasma Debio 1143 and Debio 1143-MET1 described in the protocol, PK parameters will also be calculated for serum nivolumab.

Additional descriptive statistics, in addition to the ones specified in the protocol, are included for concentration and PK parameter summaries for consistency with data presentation in previous study. For the list of all descriptive statistics, refer to section 7.6.

Efficacy Analysis Set

As per protocol, treatment failure is defined as any of the following: death, unacceptable toxicity, clinical deterioration and/or symptoms worsening. Treatment failure definition is updated and defined as any: death, unacceptable toxicity, clinical deterioration and/or symptoms worsening, *except those linked to COVID-19*.

The following category is not described in the protocol:

Category 7: Patients whose treatment had to be delayed or interrupted for reasons related to COVID-19 pandemic only and did not receive at least 25% of the planned Debio1143 dose or skipped one nivolumab infusion during cycle 1. Exposure during the first 3 treatment cycles will also be considered as part of the assessment of patients who fall into this category. Planned analysis

Due to the futility of the part B cohorts, no pooling of part A and Part B will be performed.

Document: T:\sas\Debiopharm\Debio_1143\CZA60507\Biostatistics\Documentation\SAP\SAP Text\V5

Author: XXXXXXXXXX Version Number: 5.0
Version Date: 19APR2022

Template No.: CS_TP_BS016 Revision 5
Effective Date: 01Apr2018

Reference: CS_WI_BS005

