7. GENERAL CONSIDERATIONS

7.1. REFERENCE START DATE AND STUDY DAY -

Study Day will be calculated from the reference start date and will be used to show start/stop day of assessments and events.

Reference start date is defined as the day of the first dose of any study medication, (Day 1 is the day of the first dose of any study medication).

If the date of an event is on after the reference date, the following will be calculated:

- study day = date of event – reference date + 1
- cycle day = (date of an event – date of earliest administration of Nivolumab and/or Debio 1143 in Cycle n) + 1, where date of an event < date of earliest administration of Nivolumab and/or Debio 1143 in Cycle n

In listings, an assessment date will be supported by the cycle number/day which takes the format CxDy, where Cx is the cycle number as recorded in the study exposure (nivolumab) eCRF and Dy is the cycle day.

If the date of an event is prior to the reference date, then:

- Study Day = date of event – reference date

Document: T:\sas\Debiopharm\Debio_1143\CZA60507\Biostatistics\Documentation\SAP\SAP Text\V5

Author: XXXXXXXXXX Version Number: 5.0
Version Date: 19APR2022

Template No.: CS_TP_BS016 Revision 5
Effective Date: 01Apr2018

Reference: CS_WI_BS005

In the situation where the event date is partial or missing, study day, and any corresponding durations will not be calculated.

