18.3. LABORATORY EVALUATIONS

Results from the laboratory will be included in the reporting of this study for Haematology, Chemistry, Virology and Endocrinology. A list of laboratory assessments to be included in the outputs is included in the protocol (section 8.2.2.4 and as a footnote to table 8-6: schedule of assessments).

Presentations will use SI Units.

Quantitative laboratory measurements reported as “< LLOQ”, i.e. below the lower limit of quantification (BLQ), or “>ULOQ”, i.e. above the upper limit of quantification (ULQ), will be converted to the lower limit of quantification (LLOQ) or the upper limit of quantification (ULOQ) for the purpose of quantitative summaries, but will be presented as recorded, i.e. as “< LLOQ” or “>ULOQ” in the listings.

The following summaries will be provided for each lab parameter:

- Actual and change from baseline by visit (for quantitative measurements)
- Worst on-treatment CTCAE grade for each gradable parameter

Document: T:\sas\Debiopharm\Debio_1143\CZA60507\Biostatistics\Documentation\SAP\SAP Text\V5

Author: XXXXXXXXXX Version Number: 5.0
Version Date: 19APR2022

Template No.: CS_TP_BS016 Revision 5
Effective Date: 01Apr2018

Reference: CS_WI_BS005

Copyright © 2009, 2010, 2012, 2016, 2018 IQVIA. All rights reserved. The contents of this document are confidential and proprietary to IQVIA Holdings Inc. and its subsidiaries. Unauthorized use, disclosure or reproduction is strictly prohibited.

- Shift using CTCAE grades from baseline to the worst on-treatment value
- Shift from baseline to the worst on-treatment value using the low / normal / high / (low and high) classification (only for non-gradable parameters)
- Incidence of maximum grade on treatment presented overall and by cycle, updating denominator for each cycle with the number patients receiving at least one dose of nivolumab in that cycle (only for gradable parameters)
- For patients having a grade 3/4 value:
 - Time to First Grade 3/4 Toxicity and Time to Resolution:
 - Time to recovery to grade ≤ 2
 - Time to recovery to grade ≤ 1
 - Time to full recovery (grade 0)
 - Conservative duration: (first assessment showing improvement (lower than grade 3/4) – date when analyte first graded 3/4 + 1)
 - Non-conservative duration: (last date analyte graded 3/4 (before grade ≤ 2) – date when analyte first graded 3/4 + 1)

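### Two by-cycle safety summaries in the SAP use a nivolumab-only denominator, which can leave out patients kept on Debio 1143 alone during an immune-related nivolumab hold

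*SAP*

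**What the plan says.** SAP 18.1.1 lists four presentations of TEAEs. The third, by SOC/PT and worst grade for Cycle 2 onward, is to be produced "updating denominator for each cycle with the number patients receiving at least one dose of nivolumab in that cycle". SAP 18.3 carries the same rule into one laboratory summary, for gradable parameters: "Incidence of maximum grade on treatment presented overall and by cycle, updating denominator for each cycle", again counting patients with a nivolumab dose in the cycle.

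Protocol 5.4 says that patients with immune-related AEs "may withhold nivolumab for a maximal period of up to 8 weeks" (with a one-week tolerance), and adds: "During this period, patients may continue to receive Debio 1143 as per protocol, if appropriate". The synopsis, under treatment duration, gives the same permission. The reverse is not allowed: if Debio 1143 is withheld, nivolumab is withheld too.

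Elsewhere the SAP does not tie exposure to nivolumab. The safety set (6.3) needs a dose of either drug, and section 18 puts all safety outputs except the DLT outputs on that set. While Debio 1143 is ongoing, SAP 16.1 starts a cycle on a Day 1 dose of Debio 1143.

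**The concern.** During a temporary hold, a cycle on one drug can only be a cycle on Debio 1143, and the reason named in Protocol 5.4 is immune toxicity. Removal from the denominator is therefore related to the outcome being tabulated. A patient can be in the safety set, in a started cycle and at risk of further events, and still not be counted among those at risk.

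Safety and tolerability at the RP2D is a secondary objective of Part B (Protocol 4.2.2). Cohorts have at most 15 evaluable patients, and later cycles will have fewer, so one or two patients move a percentage visibly.

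**Working it through.** The plan gives no figure on this point, so there is nothing to reproduce. Two checks apply.

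**1. Can a cycle be free of nivolumab while Debio 1143 continues?**

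- Maximum hold: 8 weeks = 56 days (Protocol 5.4). Cycle length: 28 days (Table 8-6).
- 56/28 = 2.0 cycles. With the extra week, 63/28 = 2.25 cycles.
- On 240 mg on Days 1 and 15, both infusions of a cycle must be missed before the patient leaves the denominator. One missed infusion is not enough.
- On 480 mg every 4 weeks, one missed infusion empties the cycle.

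One or two whole nivolumab-free cycles fit inside the permitted hold, depending on where in the cycle it starts.

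**2. How far can the percentage move?**

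Let N be the patients on any study drug in the cycle and k those on Debio 1143 alone, each assumed to have the event. Let x be the patients with the event among the N − k who received nivolumab.

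- Any-drug denominator: (x + k)/N
- SAP denominator, all events in the numerator: (x + k)/(N − k)
- SAP denominator, numerator limited to nivolumab-treated patients: x/(N − k)

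The values of N, k and x are assumptions. N = 15 is the cohort maximum and N = 8 stands for a thinner cycle.

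| N | k | x | Any drug | SAP, all events | SAP, matched numerator |
|---|---|---|---|---|---|
| 8 | 1 | 1 | 2/8 = 25.0% | 2/7 = 28.6% | 1/7 = 14.3% |
| 8 | 2 | 2 | 4/8 = 50.0% | 4/6 = 66.7% | 2/6 = 33.3% |
| 15 | 2 | 2 | 4/15 = 26.7% | 4/13 = 30.8% | 2/13 = 15.4% |

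For N = 15 with k from 1 to 3 and x from 0 to 2, the three columns run over 6.7–33.3%, 7.1–41.7% and 0–16.7%.

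**Direction.** With all events kept, the figure is inflated by N/(N − k), for example 8/6 = 1.33. With a matched numerator, suppose j of the k patients have the event. Then x/(N − k) falls below (x + j)/N exactly when j/k exceeds x/(N − k), that is, when the event is more frequent in the held patients than in those given nivolumab. Hence it can be too low, but need not be.

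**The case against.** **Scope.** A reader might infer that every by-cycle safety percentage is affected. The text does not support that. The bullet just before the third one in 18.1.1, "SOC/PT & worst grade (by cycle", has no such rule, and neither do the by-cycle tables of Grade 3 or higher events (18.1.3), SAEs (18.1.13) and AESIs (18.1.16). Nor do events vanish from the report, since those tables and the listings remain. This objection stands: two summaries are affected.

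**Who is affected.** Several protocol rules narrow the group. In 5.4, failing the Day 1 re-treatment criteria holds both drugs. Table 7-2 ends study treatment for many Grade 3 events. Section 7.7.2 allows otherwise prohibited drugs, including steroids above 10 mg/d, for related TEAEs only after Debio 1143 is interrupted. This stands as a limit, but it does not empty the group. The immune-related row of Table 5-3 restricts nivolumab only. Table 7-2 also withholds nivolumab in situations that need not involve high-dose steroids, such as a Grade 3 endocrinopathy on hormone replacement or a Grade 2 ocular event treated topically.

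**Timing.** The event that triggers a hold precedes the missed infusion, so by onset it may fall in an earlier cycle, when the patient was still counted. That is fair, and the SAP states no rule for assigning TEAEs to cycles. The illustration therefore assumes that the held patients have a new or worsened event in the held cycle. The point weighs less on the laboratory summary, which takes the highest grade in the cycle.

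**Numerator.** A reader might infer percentages above 100%. That requires an unrestricted numerator and many events. The SAP is silent on the numerator, and the table shells, which might settle it, are a separate document not available here.

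**Neighbouring points.** A reader might infer that cycle labels fail in held cycles, because in SAP 7.1 "Cx is the cycle number as recorded in the study exposure (nivolumab) eCRF". Without the form, nobody can tell whether it is blank then. The SAP 4.3 decision not to pool Parts A and B is a separate, openly declared change to an exploratory analysis and does not bear on these denominators.

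**Conclusion.** The concern holds for two descriptive summaries: the TEAE table by worst grade from Cycle 2 onward, and the by-cycle maximum laboratory grade. Both can leave out treated, at-risk patients for a toxicity-related reason, and the numerator is undefined. On assumed counts, a true 50.0% in a cycle of 8 could be shown as 66.7% or 33.3%; in a full cohort of 15, 26.7% could be shown as 30.8% or 15.4%. How many patients are affected cannot be learned from the documents and may be few. No decision rule or primary endpoint depends on these tables, so this is a correction of reporting, not a threat to the trial's conclusions.

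**What to change.** In the third bullet of SAP 18.1.1 and the matching bullet of SAP 18.3, define the denominator as safety-set patients who received at least one dose of Debio 1143 or nivolumab in that cycle. State that the numerator counts events or grades in the same patients. A short sentence on how a TEAE is assigned to a cycle would remove the timing ambiguity.

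The cost is SAP wording and reprogramming of two tables. Exposure to both drugs is already recorded, so no new data are needed.

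Separately, the Protocol 5.4 rule on failed Day 1 criteria, the 5.4 rule on immune-related holds and section 7.7.2 on prohibited medication should be reconciled, so that it is clear when Debio 1143 continues alone. Which rule is right is a clinical matter and is not proposed here.

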18.1.2. DLTs

DLTs are TEAEs where the question for DLTs in the eCRF is selected as “yes”. DLTs will need to be confirmed when making dose escalation decision.

An additional table will be presented showing the number of patients, by dose level, in each category with regards to number of DLTs (0, 1, ≥ 2).

A vertical bar plot will be produced showing the number of evaluable patients and the number of patients having at least one DLT.

Document: T:\sas\Debiopharm\Debio_1143\CZA60507\Biostatistics\Documentation\SAP\SAP Text\V5

Author: XXXXXXXXXX Version Number: 5.0
Version Date: 19APR2022

Template No.: CS_TP_BS016 Revision 5
Effective Date: 01Apr2018

Reference: CS_WI_BS005

Copyright © 2009, 2010, 2012, 2016, 2018 IQVIA. All rights reserved. The contents of this document are confidential and proprietary to IQVIA Holdings Inc. and its subsidiaries. Unauthorized use, disclosure or reproduction is strictly prohibited.

18.1.3. TEAEs WITH GRADE 3 OR HIGHER

TEAEs with grade 3 or higher are those events recorded on the eCRF where “NCI CTCAE Grade V5.0 Criteria” is answered as “Grade 3”, “Grade 4” or “Grade 5”.

TEAEs with grade 3 or higher will be presented by the following:

- SOC/PT and relatedness to study drugs (related to Debio 1143, related to nivolumab and related to both)
- PT and relatedness to study drugs
- SOC/PT and by cycle

18.1.4. TEAEs RELATED TO DEBIO 1143

TEAEs related to Debio 1143 are those events recorded on the eCRF where “Causal Relationship to Debio 1143” is answered as “Reasonable causal relationship”.

TEAEs related to Debio 1143 will be presented by the following:

- SOC/PT
- SOC/PT & worst grade
- SOC/PT, worst grade and by cycle
- PT & worst grade

18.1.5. TEAEs RELATED TO NIVOLUMAB

TEAEs related to nivolumab are those events recorded on the eCRF where “Causal Relationship to Nivolumab” is answered as “Reasonable causal relationship”.

TEAEs related to nivolumab will be presented by the following:

- SOC/PT
- SOC/PT & worst grade
- PT & worst grade

18.1.6. TEAEs RELATED TO BOTH DEBIO 1143 AND NIVOLUMAB

TEAEs related to both Debio 1143 and Nivolumab are those events which meet both the criteria described in sections 18.1.4 and 18.1.5.

TEAEs related to both will be presented by the following:

- SOC/PT

Document: T:\sas\Debiopharm\Debio_1143\CZA60507\Biostatistics\Documentation\SAP\SAP Text\V5

Author: ██████████ Version Number: 5.0
Version Date: 19APR2022

Template No.: CS_TP_BS016 Revision 5
Effective Date: 01Apr2018

Reference: CS_WI_BS005

- SOC/PT & worst grade
- PT & worst grade

18.1.7. TEAEs LEADING TO DOSE REDUCTION OF DEBIO 1143

TEAEs leading to dose reduction of Debio 1143 are those events recorded on the eCRF where “Action taken with Debio 1143” is answered as “Dose reduced”.

TEAEs leading to dose reduction of Debio 1143 will be presented by the following:

- SOC/PT & by cycle
- PT

18.1.8. TEAEs LEADING TO INTERRUPTION OF DEBIO 1143

TEAEs leading to interruption of Debio 1143 are those events recorded on the eCRF where “Action taken with Debio 1143” is answered as “Dose omitted” or “Treatment delayed”.

TEAEs leading to interruption of Debio 1143 will be presented by the following:

- SOC/PT & by cycle
- PT

18.1.9. TEAEs LEADING TO DISCONTINUATION OF DEBIO 1143

TEAEs leading to dose discontinuation of Debio 1143 are those events recorded on the eCRF where “Action taken with Debio 1143” is answered as “Treatment permanently discontinued”.

TEAEs leading to dose discontinuation of Debio 1143 will be presented by the following:

- SOC/PT & by cycle
- PT

